6.4.7. Seroresponse

Seroresponse is defined as $\geq 4^*LLOQ$ for those with baseline $<LLOQ$; ≥ 4 -foldrise for those with baseline $\geq LLOQ$.

Seroresponse will be derived based on two types of baselines:

- 1) Pre-vaccination (Pre-Dose 1 of the primary series)
- 2) Pre-booster baseline

Both definitions will be used when comparing seroresponse rate for all study parts.

Seroresponse based on change (fold rise) from pre-dose 1 of the primary series would be considered the primary approach of seroresponse.

For subjects without pre-Dose 1 antibody titer information, seroresponse is defined as $\geq 4^*LLOQ$ for subjects with negative SARS-CoV-2 status at their pre-dose 1 of primary series, and these subjects antibody titer will be deemed $<LLOQ$ at pre-dose 1 of primary series.

- For subjects who are without SARS-CoV-2 status information at pre-dose 1 of primary series, their pre-booster SARS-CoV-2 status will be used to impute their SARS-CoV-2 status at their pre-dose 1 of primary series.

6.5. Efficacy Analysis

Vaccine efficacy will not be formally assessed in this trial but active surveillance for COVID-19 and SARS-CoV-2 infection through weekly contact and blood draws (see SoE, table in the protocol), will be performed.

Pre-booster SARS-CoV-2 status is described in [Section 6.1](#). Pre-booster SARS-CoV-2 status, the serology test results based on Roche Elecsys assay pre-booster, the RT-PCR test results pre-booster will be summarized.

In this study, the serology test results based on Roche Elecsys assay and the RT-PCR test results will be summarized by visit.

The primary analysis population to assess incidence of symptomatic SARS-CoV-2 infection (COVID-19), asymptomatic SARS-CoV-2 infection, and SARS-CoV-2 infection is PP Efficacy Set, unless otherwise specified. FAS may be used for supportive analyses. All results will be summarized by study arm for each study part.

6.5.1. Endpoint Definition/Derivation

6.5.1.1. Derivation of SARS-CoV-2 Infection

SARS-CoV-2 infection is a combination of COVID-19 and asymptomatic SARS-CoV-2 infection. SARS-CoV-2 infection will be defined in participants by either:

- Participants with negative SARS-CoV-2 status at baseline and that becomes serology positive (as measured by *Roche Elecsys*) post baseline, OR
- Positive RT-PCR post baseline.

During the analysis, documented infection is counted starting 14 days after the dose of IP.

The date of documented infection will be the earlier of:

- Date of positive post-baseline RT-PCR result, or
- Date of positive serology test result based on bAb specific to SARS-CoV-2 nucleocapsid

The time to the first SARS-CoV-2 infection will be calculated as:

Time to the 1st SARS-CoV-2 infection = Date of the 1st documented infection – Date of injection + 1.

Cases will be counted starting 14 days after the injection, i.e. date of documented infection – Date of the injection \geq 14.

SARS-CoV-2 infection cases will also be summarized based on tests performed at least 14 days after the dose of IP.

6.5.1.2.Derivation of Asymptomatic SARS-CoV-2 Infection

This is an exploratory efficacy endpoint: the incidence of asymptomatic SARS-CoV-2 infection measured by RT-PCR of nasal swabs and/or serology tests obtained at post-baseline study visits counted starting 14 days after the injection.

Asymptomatic SARS-CoV-2 infection is identified by absence of symptoms and infections as detected by RT-PCR or serology tests. Specifically:

- Absent of COVID-19 symptoms

AND at least one from below:

- Participants with negative SARS-CoV-2 status at baseline and becomes positive (serology test result based on bAb specific to SARS-CoV-2 nucleocapsid protein) post baseline, when blood samples for immunogenicity are collected, or
- Positive RT-PCR test at scheduled or unscheduled/illness visits

The date of documented asymptomatic infection is the earlier date of positive serology test result based on bAb specific to SARS-CoV-2 nucleocapsid due to infection, or positive RT-PCR , with absence of symptoms.

The time to the asymptomatic SARS-CoV-2 infection will be calculated as:

Time to the asymptomatic SARS-CoV-2 infection = Date of asymptomatic SARS-CoV-2 infection – Date of injection + 1.

6.5.1.3.Derivation of Symptomatic SARS-CoV-2 Infection (COVID-19)

This is an exploratory efficacy endpoint: the incidence of the first occurrence of symptomatic SARS-CoV-2 infection measured by RT-PCR of nasal swabs counted starting 14 days after the injection. Surveillance for COVID-19 symptoms will be conducted via weekly contact and blood draw. Subjects reporting COVID-19 symptoms will be arranged an illness visit to collect an NP swab.

Two definitions of symptomatic SARS-CoV-2 Infection, COVID-19, will be evaluated:

1. Primary case definition per the P301 (COVE) study: Cases are defined as participants meeting clinical criteria based on both symptoms for COVID-19 and positive RT-PCR test results as described in [Table 4-1](#).
2. Secondary case definition based on CDC criteria: Cases are defined as participants with symptomatic disease based on the criteria defined by the CDC (<https://www.cdc.gov/coronavirus/2019-ncov/symptoms-testing/symptoms.html>).

Table 4-1: Derivation of primary case definition of COVID-19

COVID-19 (per the P301 COVE study)	
Post-baseline PCR results	Positive, AND
Systemic Symptoms	at least TWO of the following systemic symptoms : Fever ($\geq 38^{\circ}\text{C}/\geq 100.4^{\circ}\text{F}$), chills, muscle and/or body aches (not related to exercise), headache, sore throat, new loss of taste/smell; OR
Respiratory Symptoms	at least ONE of the following respiratory signs/symptoms: cough, shortness of breath and/or difficulty breathing, OR clinical or radiographical evidence of pneumonia.

Table 4-2: Derivation for secondary case definition of COVID-19

COVID-19 (CDC criteria)	
Post-baseline PCR results	Positive, AND
Systemic and Respiratory Symptoms	at least ONE of the following systemic or respiratory symptoms : Fever ($\geq 38^{\circ}\text{C}/\geq 100.4^{\circ}\text{F}$), chills, cough, shortness of breath and/or difficulty

	breathing, fatigue, muscle and/or body aches (not related to exercise), headache, new loss of taste/smell, sore throat, congestion, runny nose, nausea, vomiting, or diarrhea.
--	--

The date of documented COVID-19 (case) will be the later date of eligible symptom and date of positive PCR test. Specifically, the date of documented COVID-19 will be the later date of the following two dates (date of positive PCR test, and the date of eligible symptom(s)), and the two dates should be within 14 days of each other.

The time to the first occurrence of COVID-19 will be calculated as:

Time to the 1st occurrence of COVID-19 = Date of documented COVID-19 – Date of injection + 1.

Cases will be counted starting 14 days after the injection, i.e. date of documented COVID-19 - Date of the injection \geq 14.

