Cases are defined as participants meeting clinical criteria based both on symptoms for COVID-19 and on RT-PCR detection of SARS-CoV-2 from samples collected within 72 hours of the study participant reporting symptoms meeting the definition of COVID-19. Participants who are hospitalized for COVID-19 without the opportunity for a clinic visit will also be considered cases, assuming that the symptomatology criteria for COVID-19 are met and a respiratory sample is positive for SARS-CoV-2 by PCR at a Clinical Laboratory Improvement Amendments (CLIA)-certified or CLIA-certified waiver laboratory. Investigators are encouraged to try to obtain a respiratory sample during the course of hospitalization for submission to the study central laboratory, if feasible.

Symptomatic COVID-19 is defined by the presence of one of the CDC-listed symptoms ([CDC 2020](#)) and a positive RT-PCR test on a respiratory sample. Asymptomatic SARS-CoV-2 infection is defined as a positive RT-PCR test on a respiratory sample in the absence of symptoms or a positive serologic test for antinucleocapsid antibody after a negative test result at the time of enrollment, with the serologic assay detecting previously resolved SARS-CoV-2 infections that may have occurred between visits, and the RT-PCR to detect active viral infection at the time of a visit. If participants are confirmed to have SARS-CoV-2 infection and are symptomatic or asymptomatic, the investigator will notify the participants' primary care physicians of the diagnosis and the local public health authorities as required per local regulations.

If the participant had known exposure to COVID-19 (eg, exposure to someone with a confirmed case of COVID-19), it will be captured in the COVID-19 exposure form, and the participant will continue to follow all remaining study assessments as scheduled. Likewise, participants with a confirmed case of COVID-19 will continue to follow all remaining study assessments as scheduled.

Any confirmed symptomatic COVID-19 infection occurring in participants will be captured as an MAAE along with relevant concomitant medications and details about severity, seriousness, and outcome.

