7.2. Immunogenicity Assessments

Blood samples for immunogenicity assessments will be collected at the time points indicated in the SoE ([Table 17](#), [Table 18](#), [Table 19](#), and [Table 20](#)).

Sample aliquots will be designed to ensure that backup samples are available and that vial volumes are likely to be adequate for future testing needs. The actual time and date of each

sample collected will be recorded in the eCRF. Handling and preparation of the samples for analysis, as well as shipping and storage requirements, will be provided in a separate study manual.

Measurement of bAb and nAb levels will be performed in a laboratory designated by the Sponsor.

According to the ICF ([Section 10.2.6](#)), excess serum from immunogenicity testing may be used for future research, which may be performed at the discretion of the Sponsor to further characterize the immune response to SARS-CoV-2, additional assay development, and the immune response across CoV.

Nasopharyngeal swab samples to be collected are also shown ([Table 12](#) and [Table 13](#)).

Table 12: Blood and Nasopharyngeal Swab Sampling for Parts A.1, B, C, D, F, and G

Sample Name	D1 (Baseline)	D15	D29	D91 (Part F and Part G only)	D181	D366	UNS / Illness
Anti-SARS-CoV-2	1		1	1	1	1	1
Immunogenicity	1	1	1	1	1	1	1
RT-PCR/Sequencing	1		1	1	1		1
BioFire 2.1							1
PBMC may be collected for a subset of participants at selected sites	1	1	1	1			

Abbreviations: D =day; N/A = not applicable; NP = nasopharyngeal; PBMC = Peripheral Blood Mononuclear Cells; RT-PCR = reverse transcriptase polymerase chain reaction; SST = serum separator tube; UNS = unscheduled visit.

Table 13: Blood and Nasopharyngeal Swab Sampling for Parts A.2, H, and J

Sample Name	D1 (Baseline)	D15	D29	D91	D181	UNS / Illness
Anti-SARS-CoV-2	1		1	1	1	1
Immunogenicity	1	1	1	1	1	1
RT-PCR/Sequencing	1		1	1	1	1
BioFire 2.1						1

Abbreviations: D =day; N/A = not applicable; NP = nasopharyngeal; PBMC = Peripheral Blood Mononuclear Cells; RT-PCR = reverse transcriptase polymerase chain reaction; SST = serum separator tube; UNS = unscheduled visit.

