10. SUPPORTING DOCUMENTATION AND OPERATIONAL CONSIDERATIONS

10.1. APPENDIX 1: Schedule of Events

Table 17: Schedule of Events for Parts A.1, B, C, D, F, and G

Visit Number	Screening ¹	V1		V2	V3	V3a			V4			V5	UNS
Type of Visit	C	C	SC	C	C	C	SFU (eDiary)	SFU (SC)	C	SFU (eDiary)	SFU (SC)	C	C
Month Timepoint	M0	M0			M1	M3			M6			M12	--
Study Visit Day	D0 ¹	D1 ¹	D8	D15	D29	D91 (Parts F and G only)	Every 2 weeks D36–D162 ²	Every 2 weeks D43–D169	D181	Every 2 weeks D202–D342 ²	Every 2 weeks D209–D349	D366	
Window Allowance (Days)	-7	0	+3	±3	-7	±7	±2	±3	±14	±2	±3	±14	--
Days Since Booster Injection		0	7	14	28	90	--		180	--		365	--
Informed consent form	X												
Study injection (including 30-minute post-dosing observation period)		X											
Confirm participant meets inclusion and exclusion criteria	X												
Physical examination including vital signs ³	X	X			X	X			X			X	X
Pregnancy testing		X											
Blood for SARS-CoV-2 serology (antinucleocapsid antibody)		X			X	X			X			X	X
Blood for immune response to vaccination (binding and neutralizing antibody) ⁴		X		X	X	X			X			X	X

Visit Number	Screening ¹	V1		V2	V3	V3a			V4			V5	UNS
Type of Visit	C	C	SC	C	C	C	SFU (eDiary)	SFU (SC)	C	SFU (eDiary)	SFU (SC)	C	C
Month Timepoint	M0	M0			M1	M3			M6			M12	--
Study Visit Day	D0 ¹	D1 ¹	D8	D15	D29	D91 (Parts F and G only)	Every 2 weeks D36–D162 ²	Every 2 weeks D43–D169	D181	Every 2 weeks D202–D342 ²	Every 2 weeks D209–D349	D366	
Window Allowance (Days)	-7	0	+3	±3	-7	±7	±2	±3	±14	±2	±3	±14	--
Days Since Booster Injection		0	7	14	28	90	--		180	--		365	--
Nasopharyngeal swab sample for SARS-CoV-2 ⁴		X			X	X			X			X	X ⁵
eDiary activation for recording solicited local and systemic reactogenicity adverse reactions (7 days)		X											
Review of eDiary			X										
Follow-up safety calls ⁶			X					X			X		
Recording of unsolicited AEs		X	X	X	X								
Recording of MAAEs and concomitant medications relevant to or for the treatment of the MAAE ⁷		X	X	X	X	X	X	X	X	X	X	X	
Recording of SAEs and concomitant medications relevant to or for the treatment of the SAE ⁷		X	X	X	X	X	X	X	X	X	X	X	
Recording of AESI		X	X	X	X	X	X	X	X	X	X	X	

Visit Number	Screening ¹	V1		V2	V3	V3a			V4			V5	UNS
Type of Visit	C	C	SC	C	C	C	SFU (eDiary)	SFU (SC)	C	SFU (eDiary)	SFU (SC)	C	C
Month Timepoint	M0	M0			M1	M3			M6			M12	--
Study Visit Day	D0 ¹	D1 ¹	D8	D15	D29	D91 (Parts F and G only)	Every 2 weeks D36–D162 ²	Every 2 weeks D43–D169	D181	Every 2 weeks D202–D342 ²	Every 2 weeks D209–D349	D366	

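### The 14-day start for counting infections does not operate for serology-only cases first detected at Day 29, because they are dated by the test and not by acquisition

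*SAP*

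**What the plan says.** SAP 6.5.1.1 sets the start of counting: "During the analysis, documented infection is counted starting 14 days after the dose of IP". It repeats the rule as a date difference: "Cases will be counted starting 14 days after the injection, i.e. date of documented infection" less the injection date must be at least 14 days. The documented date is the earlier of two dates, a positive post-baseline RT-PCR or the "Date of positive serology test result based on bAb specific to SARS-CoV-2 nucleocapsid". A further summary is promised: "SARS-CoV-2 infection cases will also be summarized based on tests performed at least 14 days after the dose of IP".

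SAP 6.5.1.2 treats asymptomatic infection alike: "The date of documented asymptomatic infection is the earlier date of positive serology test result based on bAb specific to SARS-CoV-2 nucleocapsid due to infection". The alternative is a positive RT-PCR without symptoms. It also counts from 14 days after the injection.

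In the Protocol's schedules of events (Section 10.1), the row "Blood for SARS-CoV-2 serology (antinucleocapsid antibody)" is marked at Day 1 and next at Day 29. Day 15 is blank. Tables 12 and 13 in Protocol 7.2 show the same gap. Protocol 3.2 puts the first scheduled post-dose swab at Day 29 too. On what the blood test measures, Protocol 7.1.6 describes RT-PCR as finding active infection at a visit, "with the serologic assay detecting previously resolved SARS-CoV-2 infections that may have occurred between visits".

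**The concern.** By the Protocol's own account, a positive anti-nucleocapsid test means infection at some time since the last negative sample. The SAP uses the test date as the infection date and then applies a 14-day cut to it. The first scheduled test after the dose falls well beyond 14 days, so the cut cannot remove anyone at that visit.

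At stake is the meaning of the asymptomatic and any-infection tables. They are to be read as infections from 14 days after the booster, but they will include an unknown number acquired earlier. The any-infection count can also treat the same early infection in two ways. If it is swabbed on day 5 it is dated day 5 and left out; if it is not swabbed it is counted at Day 29. SAP 6.5.2 plans incidence rates with exact confidence intervals, reported by arm, and the arms enrolled in different periods (SAP 6.4.3 gives February 2022 for the Part F mRNA-1273 arm and August 2022 for Part H). The number of misplaced cases need not be similar across arms.

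**Working it through.** The plan attaches no event count, power or rate to this endpoint, so there is no figure to reproduce. The check is date arithmetic followed by an illustration of size.

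**Inputs**
- Counting rule: documented date minus injection date of at least 14 days (SAP 6.5.1.1).
- Day 29 sample: 28 days after injection, with a window of -7 days (schedules of events). SAP 5.3 accepts 21 to 42 days for the immunogenicity set, so 42 is used as a late draw.
- Follow-up: 180 days (Parts A.2, H, J) or 365 days (Parts A.1, B, C, D, F, G).
- Delay L from infection to seropositivity: not given in either document. Assumed range 0 to 14 days.
- Hazard: assumed constant after the dose. Only post-dose infections are counted.

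**Step 1: does the rule exclude any Day 29 conversion?**
Nominal draw: 29 - 1 = 28, which is at least 14. Earliest draw: 28 - 7 = 21, also at least 14. No conversion at the scheduled Day 29 visit can fail the rule on its serology date.

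**Step 2: what share of those conversions was acquired before day 14?**
With a draw d days after injection, the post-dose infections already seropositive were acquired between day 0 and day d - L. The share acquired before day 14 is min(14, d - L)/(d - L).

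| Draw d | L = 0 | L = 7 | L = 14 |
|---|---|---|---|
| 21 days | 14/21 = 67% | 14/14 = 100% | 7/7 = 100% |
| 28 days | 14/28 = 50% | 14/21 = 67% | 14/14 = 100% |
| 42 days | 14/42 = 33% | 14/35 = 40% | 14/28 = 50% |

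**Step 3: what share of all serology-only cases is that?**
With a 28-day draw and L up to 14, every infection acquired before day 14 is seropositive by the draw. The share over follow-up of length T is 14/(T - L).
- 6-month parts: 14/180 = 7.8% to 14/166 = 8.4%.
- 12-month parts: 14/365 = 3.8% to 14/351 = 4.0%.

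**Step 4: does another provision repair it?**
- The second summary in SAP 6.5.1.1 also selects on test date. It may readmit an early RT-PCR case through its Day 29 serology.
- SAP 6.5 summarises serology and RT-PCR results by visit. That shows Day 29 positives but leaves the case counts and rates unchanged.
- SAP 6.5.3 allows sensitivity analyses with other criteria and start times. They are optional, and no rule for serology-only cases is given.

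**The case against.** The strongest reply is that little depends on this. The endpoint is exploratory, and both documents say that efficacy is not formally assessed. The results are descriptive summaries by arm, with no hypothesis attached. That stands, and it limits the severity.

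Second, the SAP speaks of documented infection and defines it by test date, so it never claims acquisition after day 14. This is a fair reading of the definition. But a 14-day cut on a date that always exceeds 14 days does nothing at that visit, and a reader of the table will take it as an exclusion that was applied.

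Third, SAP 6.5.2 starts person-time at injection, so a serology numerator reaching back to Day 1 broadly matches its denominator. This stands for the crude rate, which need not be inflated. It does not rescue the from-day-14 label.

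Fourth, the swabbed/unswabbed contrast is narrow for the asymptomatic endpoint. No swab is scheduled between Day 1 and Day 29, and earlier swabs are mainly prompted by symptoms. That also stands; the contrast applies chiefly to the any-infection count.

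Fifth, Day 29 is the first scheduled anti-nucleocapsid sample, not the only possible one. Unscheduled visits can draw serology earlier. Protocol 3.1 mentions antibody testing at Day 15 in Part J, and SAP 6.5.1.2 ties serology to immunogenicity blood draws, although Tables 13 and 20 leave the anti-nucleocapsid row blank at Day 15. A conversion at a nominal Day 15 visit would be exactly 14 days after injection. It would pass the rule although acquired by that day.

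**Conclusion.** The point holds as a derivation that does not do what it states. For seroconversions first seen at the scheduled Day 29 visit without an earlier positive RT-PCR, the 14-day exclusion removes nobody. That part follows from the documents alone. The size rests on constant hazard and an assumed delay: from half to all of such conversions at a 28-day draw, and from a third to a half at 42 days. Over follow-up it is about 8% (6-month parts) or 4% (12-month parts) of serology-only cases. The correction is minor to moderate.

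Three stronger readings are not supported.
- A reader might infer that most Day 29 conversions predate day 14. With no delay and a 28-day draw the figure is 50%, and it is lower for a later draw. Anything above half needs an assumed delay or an early draw.
- A reader might add infections acquired just before injection that convert later. With a 7-day delay this gives 21/28 = 75%. If all Day 1-29 conversions were misplaced, the follow-up shares would reach 28/180 = 15.6% and 28/365 = 7.7%. But the PP Efficacy Set requires a negative baseline RT-PCR, and the exclusion criteria cover recent close contact, recent known infection and acute illness. These remove some of those infections, so full hazard before the dose is not justified.
- A reader might infer that a vaccine-effect estimate is biased. No such estimate is planned.

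**What to change.** In the asymptomatic and any-infection tables, report participants who are anti-nucleocapsid negative at Day 1, positive at Day 29 and without a dated RT-PCR as a separate row: *infection between Day 1 and Day 29, timing not determined*. Present the from-day-14 count and rate with and without them. The version without them should require, for serology-only cases, a negative anti-nucleocapsid sample at least 14 days after injection (in practice a negative Day 29 sample), and should start serology person-time at that sample. State the rule in SAP 6.5.1.1, 6.5.1.2 and 6.5.2.

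The cost is a derivation change on data already collected. The loss in the restricted version is not small: it drops true day 14-28 infections already seropositive at Day 29, up to about half of Day 29 conversions at a 28-day draw if there is no delay. It also gives the serology component a later time origin than RT-PCR, which the table should note. For these reasons both versions should be shown, and neither should replace the other.

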6.5.2. Analysis Method

The number and percentage of subjects who had each type of event (ie, an asymptomatic or a symptomatic SARS-CoV-2 infection) will be summarized in the PP Efficacy Set.

The incidence rate of each type of event will be calculated as the number of cases divided by the total person-time. The 95% CI of the incidence rate will be calculated using the exact method (Poisson distribution) and adjusted by person-time.

Person-time is defined as the total time from injection date to the date of event, last date of study participation, or censoring time, whichever is earlier.

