8.5.2. Efficacy Analysis

This study is not designed to assess efficacy. Descriptive summaries of symptomatic COVID-19 disease, asymptomatic SARS-CoV-2 infection, as well as SARS-CoV-2 infections regardless of symptoms will be provided for each study arm. analyses will be performed using PP Set for Efficacy.

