With approximately 375 participants exposed to 50 μ g mRNA-1273.214, there is at least 90% probability in this group to observe 1 participant reporting an AE if the true rate of AEs is 1%.

Part H

The target enrollment is approximately 500 participants for 50 μ g mRNA1273.222. Assuming 40% of participants will be excluded from the PPIS-Neg (due to a SARS-CoV-2 infection pre-booster), with approximately 300 participants in 50 μ g mRNA1273.222 and 260 participants in 50 μ g mRNA-1273 (Part F, Cohort 2-50 μ g mRNA-1273) in the PPIS and SARS-CoV-2 negative, there is approximately 60% power to demonstrate the primary immunogenicity objectives with alpha of 0.05 (2-sided) at Day 29. The assumptions are: the true GMR (mRNA-1273.222 second booster vs. 50 μ g mRNA-1273 second booster) against Omicron BA.4/5 is 1.5, GMR (mRNA-1273.222 second booster vs. mRNA-1273 second booster) against ancestral SARS-CoV-2 D614G is 1, the standard deviation of the log-transformed titer is 1.5, and the non-inferiority margin for GMR is 1.5. The true SRR against Omicron BA.4/5 after mRNA-1273.222 as a second booster dose is 95% (same assumption for 50 μ g mRNA-1273), and non-inferiority margin for SRR difference against Omicron BA.4/5 is 5%. The true SRR against ancestral SARS-CoV-2 D614G after mRNA-1273.222 as a second booster dose is 95% (same assumption for 50 μ g mRNA-1273), and the non-inferiority margin for SRR difference against ancestral SARS-CoV-2 D614G is 10%.

With approximately 500 participants exposed to 50 μ g mRNA-1273.222, there is at least 90% probability in this group to observe 1 participant reporting an AE if the true rate of AEs is 1%.

Part J

The sample size for Part J is not driven by statistical assumptions for formal hypothesis testing. The number of proposed participants is considered sufficient to provide a descriptive summary of the safety and immunogenicity of each treatment arm.

The target enrollment is approximately 100 participants who will be randomized in a 1:1 ratio to receive either mRNA-1273.815 (50 μ g) or mRNA-1273.231 (50 μ g).

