6.5.3. Sensitivity Analysis

Sensitivity analysis for the efficacy endpoints may be performed with the same methods described above based on the FAS and with cases counted using different criteria and starting at different time points.

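### Symptomatic COVID-19 cases count from 14 days after injection but person-time runs from injection, so at full follow-up the rate is about 8% (6-month parts) or 4% (12-month parts) below the rate over the counting window

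*SAP*

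**What the plan says.** SAP 6.5.1.3 defines the endpoint as the first "symptomatic SARS-CoV-2 infection measured by RT-PCR of nasal swabs counted starting 14 days after the injection". It repeats the rule after the two case definitions: "Cases will be counted starting 14 days after the injection, i.e. date of documented COVID-19", with the difference from the injection date required to be at least 14 days. The rule covers both the COVE-based and the CDC-based definition.

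SAP 6.5.2 gives the rate: "The incidence rate of each type of event will be calculated as the number of cases divided by the total person-time". Its denominator is defined separately: "Person-time is defined as the total time from injection date to the date of event, last date of study participation, or censoring time", whichever comes first. Nothing in the section takes the first 14 days out. The interval is an exact Poisson interval scaled by the same person-time.

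SAP 6.5.3 allows optional sensitivity analyses "with cases counted using different criteria and starting at different time points", by the same methods. It does not mention moving the start of person-time.

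Follow-up is 6 months (Day 181) for Parts A.2, H and J and 12 months (Day 366) for Parts A.1, B, C, D, E, F and G (SAP 6.2.1 and 6.8). SAP 6.1 censors effectiveness data at an off-study COVID-19 vaccine. The protocol supplies no person-time rule of its own. Section 8.5.2 promises only descriptive summaries and says "This study is not designed to assess efficacy".

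**The concern.** An incidence rate is normally read as events per unit of time in which an event could have been recorded. Here the numerator opens 14 days after injection and the denominator opens at injection. The extra 14 days per participant can only lower the rate. The error always runs in one direction, does not shrink as arms grow, and is about twice as large in the 6-month parts as in the 12-month parts, which go into the same final report.

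There is also a smaller gap. Person-time ends at the event, but the text does not say whether a symptomatic episode before day 14, which is not counted, ends it. Two programmers could reasonably differ.

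What is at stake is the accuracy of a descriptive rate. No hypothesis rests on it.

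**Working it through.** The documents state no incidence rate or person-time total, so there is no planned figure to reproduce. The check works from the definitions.

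**Inputs**
- Case counting opens 14 days after injection (SAP 6.5.1.3).
- Person-time opens at injection (SAP 6.5.2).
- Full follow-up T is 180 days (Day 181) or 365 days (Day 366) (SAP 6.8).

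**Basic shift.** With low incidence and full follow-up:
- rate as written = cases / (N × T)
- rate over the counting window = cases / (N × (T − 14))
- shortfall = 1 − (T − 14)/T = 14/T

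6-month parts: 14/180 = 7.8%. 12-month parts: 14/365 = 3.8%. Across the ±14-day window on the last visit the ranges are 14/194 to 14/166 = 7.2% to 8.4%, and 14/379 to 14/351 = 3.7% to 4.0%.

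**Example.** Take 300 participants with full follow-up and 15 cases. The 300 is Part H's 500 less 40% (SAP 4.3: "40% of participants will be excluded from the PPIS-Neg"). That figure is for the immunogenicity set and is assumed similar for the PP Efficacy Set. The same 300 is used at 365 days for comparison. The 15 cases are assumed, and person-time lost after events is ignored. Person-years = 300 × days / 365.25.

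| Follow-up | Denominator | Person-years | Rate per 1000 person-years (95% CI) |
|---|---|---|---|
| 180 days | from injection | 147.8 | 101.5 (56.8 to 167.3) |
| 180 days | from day 14 | 136.3 | 110.0 (61.6 to 181.5) |
| 365 days | from injection | 299.8 | 50.0 (28.0 to 82.5) |
| 365 days | from day 14 | 288.3 | 52.0 (29.1 to 85.8) |

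**Against sampling error.** The relative Poisson standard error is about 1/√cases. It equals the shift at 1/0.0778² ≈ 165 cases (6-month parts) or 1/0.0384² ≈ 680 cases (12-month parts) in one arm. With 15 cases the exact interval spans −44% to +65% of the rate.

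**Under a constant hazard h**, with an uncounted early event ending person-time:
- cases per participant = exp(−14h) − exp(−hT)
- person-time per participant = (1 − exp(−hT))/h
- rate as written / h = (exp(−14h) − exp(−hT)) / (1 − exp(−hT))

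For assumed cumulative incidence of 2% to 30%, this ratio falls from 0.9215 to 0.9088 at T = 180 (7.9% to 9.1% low) and from 0.9613 to 0.9547 at T = 365 (3.9% to 4.5% low). Starting person-time at day 14 among those event-free gives 1.0000 throughout.

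**With earlier censoring** (assumed: 25% or 50% of a part censored at day 90):
- T = 180: mean follow-up 157.5 or 135 days, giving 14/157.5 = 8.9% or 14/135 = 10.4%.
- T = 365: mean follow-up 296.25 or 227.5 days, giving 14/296.25 = 4.7% or 14/227.5 = 6.2%.

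**Why only the symptomatic rate.** SAP 6.5.1.1 also says that "documented infection is counted starting 14 days after the dose of IP". But after Day 1, serology and scheduled swabs are first taken at Day 29 with a −7-day window (Protocol Schedule of Events), so no earlier than 21 days after injection. The 14-day rule therefore removes almost none of those cases. Symptomatic cases come from illness visits at any time, so early ones really are excluded.

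**The case against.** **Nothing depends on the rate.** The endpoint is exploratory, no rates are tested, and the counts and percentages listed first in 6.5.2 are untouched. The 680 cases needed for a 3.8% shift to reach one standard error exceed every planned arm (at most about 584). All of this stands, and it is why the point is minor.

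**The origin is stated openly.** The SAP also measures time to first COVID-19 from injection, so counted cases per unit of time since injection is a defined quantity. It is low only as an estimate of the rate over the counting window. That is fair, and the claim is worded that way. But the SAP does not say it wants the other quantity, and most readers will assume that numerator and denominator cover the same period.

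**The composite infection endpoint has part of the same problem.** Under SAP 6.5.1.1 an illness-visit PCR positive before day 14 is dropped from overall infection too. This is true. It makes the symptomatic claim narrow but does not make it wrong.

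**The percentages assume full follow-up.** Censoring at an off-study vaccine, or leaving Part A.1 early for Part A.2, would shorten it. This also stands, and it enlarges the shift.

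**The counted event may be the one meant to end person-time.** That reading is possible. The issue is small: letting early events end person-time changed the shortfall by about 0.3 percentage points or less compared with a cohort without early events.

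**6.5.3 could count cases from injection**, which would match the denominator. It is optional and leaves the main rate as it is.

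**Conclusion.** The mismatch is in the current SAP text and the concern holds. Relative to the rate over the period in which a case can count, the symptomatic COVID-19 rate and both confidence limits are low by 7.8% in Parts A.2, H and J and by 3.8% in Parts A.1 and B to G. These figures assume low incidence and full follow-up. Higher incidence or earlier censoring raises them, to about 10% and 6% in the scenarios shown. Those scenarios rest on assumptions that the documents do not supply. The consequence is a small, one-directional misstatement of a descriptive rate, below sampling error at plausible case numbers. Severity is minor.

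**What to change.** In SAP 6.5.2, for symptomatic COVID-19 under both case definitions, start person-time 14 days after injection among participants who are then event-free and still under follow-up. State that an earlier symptomatic event removes the participant from that risk set. In 6.5.3, require that any change in when case counting starts moves the start of person-time with it.

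The counting rule for infections dated by serology or a scheduled test can stay as it is. Footnote the person-time origin in every incidence table. This matters most for overall infection, which mixes illness-visit and scheduled-test cases and would otherwise have a different denominator from the symptomatic rate without explanation.

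The cost is one or two sentences, a small programming change on data already collected, and the footnotes. Denominators become slightly smaller, and a few participants with early events leave the symptomatic risk set.
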